2.1 Assessment and management of risk

RISKS OF EXPANSION DUROPLASTY: Expansion duroplasty has been reported in two case series of patients with acute, severe TSCI [Phang et al., 2015; Rooshenas et al., 2019], despite it being performed in centres worldwide. This procedure is widely performed in patients with Chiari malformation to decompress the crano-cervical junction [Chotai et al., 2014; De Vlieger et al., 2019; Del Gaudio et al., 2018; Dlouhy et al., 2018; Elhadji Cheikh Ndiaye et al., 2019; Lin et al., 2018]. Experience from adult TSCI and Chiari patients from 2010-9 (Table below) shows that the commonest complications are CSF-related, i.e. CSF leak through the wound, which resolves with lumbar CSF drainage for 5 – 10 days, and pseudomeningocele, which resolves spontaneously in TSCI but requires re-operation in 1 % of Chiari patients. The incidence of wound infection is low (<1 %) and easily treated with antibiotics. The serious complication of septic meningitis is rare, i.e. not observed in these series. 9 % of Chiari patients develop aseptic meningitis, a benign condition not reported in duroplasty for TSCI. Because DISCUS only includes patients with cervical TSCI, CSF leak and pseudomeningocele could be reduced by sitting the patient at 45° for a week to limit cervical CSF pressure. The Table below shows the complications of expansion duroplasty for TSCI and for Chiari I malformation. Together, these findings indicate that duroplasty in the cervical region is safe.

COMPLICATION	PATIENTS NO.	%	COMMENT
Duroplasty for TSCI [Phang et al., 2015; Zhu et al., 2019]			
CSF leak	4 / 26	10	Treated successfully with lumbar drain
Wound infection	0 / 26	0	
Meningitis (septic)	0 / 26	0	
Pseudomeningocele	5 / 26	19	All resolved at 6 month MRI
Chiari I malformation [Chotai et al., 2014; De Vlieger et al., 2019; Del Gaudio et al., 2018; Dlouhy et al., 2018; Elhadji Cheikh Ndiaye et al., 2019; Lin et al., 2018]			
CSF leak	9 / 277	3	Treated with lumbar drain
Wound infection	4 / 277	1	Successfully treated with antibiotics
Meningitis (NB. aseptic)	24 / 277	9	Self-limiting, responds to steroids
Meningitis (septic)	0 / 277	0	
Pseudomeningocele	10 / 277	4	3 patients required re-operation

REDUCING RISKS OF DUROPLASTY: Several technical nuances may minimise the risks of infection, CSF leak and pseudomeningocele:

1. Use of nylon sutures for skin closure, which are more watertight than staples.
2. Applying a waterproof film dressing (e.g. Ioban®, which is a betadine impregnated adhesive dressing) over the wound for one week.
3. Postoperative intravenous antibiotic prophylaxis dictated by local policy.
4. Placing the wound drain *in situ* on gravity (rather than suction) for one week.
5. We discourage use of Tisseel glue, which is widely used in neurosurgery to reduce CSF leak, because this product expands and may thus itself cause spinal cord compression.
6. Sitting up the patient to >45° for a week to reduce cervical CSF pressure.
7. Removing the sutures at two weeks.
8. Suturing the dural patch to dura, rather than merely applying the duroplasty without suturing it.
9. Sutures to tighten the skin around the probes to reduce CSF leak (mechanistic studies).

The above measures will be discussed with the surgeons at each participating site and will be part of the online training course for participating centres but will not be imposed. Patient management will be left to the local clinical teams. These data will be documented in the CRF.

RISKS OF ISP AND MD MONITORING: In 2018, we published the safety profile of injury site monitoring for up to a week in a cohort of 42 AIS A – C TSCI patients (including cervical and thoracic injuries) treated at St. George's Hospital in London (Table below). The most common complications are CSF related and easy to manage by adding extra sutures to the wound or spontaneously resolve. These findings suggest that injury site monitoring in TSCI patients is a safe technique.

COMPLICATION	PATIENTS NO.	%	COMMENTS
CSF leak	3 / 42	7	Resolved by wound re-suturing
Wound infection or breakdown	0 / 42	0	
Meningitis (septic)	0 / 42	0	
Pseudomeningocele	8 / 42	19	All resolved at 6 month MRI
Probe displacement	1 / 42	2	
Neurological deterioration	0 / 42	0	
Haematoma	0 / 42	0	

TRIAL SAFETY: DISCUS will run in accordance with OCTRU's Standard Operating Procedures (SOPs) and operational policies, which adhere to all applicable UK regulatory requirements. The trial will be overseen by a DSMC and a TSC. The project will also be monitored by the sponsor (City St George's, University of London).

The DISCUS trial is categorised as:

- ~~Type A = No higher than the risk of standard medical care~~
- ~~Type B = Somewhat higher than the risk of standard medical care~~
- ~~Type C = Markedly higher than the risk of standard medical care~~

3 OBJECTIVES AND OUTCOME MEASURES/ENDPOINTS

3.1 Primary objective

PRIMARY OBJECTIVE: To determine if, in patients with severe cervical TSCI, bony + dural decompression improves AMS at 6 months compared with bony decompression alone.

POPULATION: We aim to recruit 222 adults with acute, severe cervical TSCI to achieve 85% study power. We may increase recruitment to 260 patients to achieve 90% power, dependent on recruitment from international sites.

Note: We exclude thoracic TSCIs because most have severe injuries with complete paralysis without any significant spontaneous motor recovery because the AIS motor scores are not sensitive to segmental recovery in the thoracic region.

INTERVENTION: Surgery (approach, instrumentation) is at the surgeon's discretion, but will include laminectomy spanning the length of swollen cord on the pre-operative MRI. Patients will have dorsal duroplasty by suturing an elliptical patch of artificial dura approximately 1 cm longer than the dural incision and approximately 2 cm wide to the dural edge. We recommend that a wound drain be placed on gravity and the skin sutured and covered with waterproof adhesive film dressing such as loban,

Note: loban is an iodine impregnated dressing that minimises the risk of wound infection and of CSF leak.

The wound drain and dressing is typically removed at 1 week and the sutures at 2 weeks. CSF leak is normally treated by placing extra sutures or a lumbar drain.

CONTROL: Standard of care surgery to include laminectomy.

OUTCOME: Improvement in AIS motor score at 6 months compared with AMS at baseline (Δ AMS).

TIMECOURSE: This project will last for a total of 96 months. Patients will be followed for 12 months after randomisation.

There will be formal stop/go review in month 15, (i.e. after 9 months of recruitment) to ensure a minimum of 5 patients have been randomised from a minimum of two centres. If the target is met, the trial will continue to completion. This 15-month formal stop/go criterion is a contractual agreement with the NIHR. One TSC meeting will be held at month 12-14 (i.e. before the formal stop/go review) and yearly thereafter unless an emergency meeting is required. The TSC will also receive information from the QRI that may require further meetings depending on recruitment.

3.2 Secondary objectives

1 (Neurology): To determine if, in patients with severe cervical TSCI, bony + dural decompression improves neurological outcome as defined by the International Standards for Neurological Classification of Spinal Cord Injury (ISNCSCI).

2 (Function): To determine if, in patients with severe cervical TSCI, bony + dural decompression improves functional outcomes at 6 months compared with bony decompression alone.

3 (Quality of life): To determine if, in patients with severe cervical TSCI, bony + dural decompression improves HRQoL at 6 and 12 months compared with bony decompression alone.

4 (Mechanism): To determine if, in patients with severe cervical TSCI, bony + dural decompression improves MRI features, improves spinal cord perfusion and reduces spinal cord inflammation at the injury site, compared with bony decompression alone.

5 (Safety): To determine if, in patients with severe cervical TSCI, bony + dural decompression is safe.

3.3 Outcome measures/endpoints

PRIMARY OUTCOME: Change in AIS motor score at 6 months versus baseline (Δ AMS).

The primary outcome is a standardised tool. The 2019 AIS ISNCSCI is a validated clinician-administered scale which is used to classify severity of injury in individuals with TSCI, taking around 30 – 60 minutes to complete. It is widely used in clinical and research settings to fully assess sensory and motor functioning and level of injury in TSCI patients. It has high inter- and intra-rater (ICC > 0.99) reliabilities and strong correlations ($r > 0.9$) with functional scores including Quadriplegia Index of Function (QIF) and Functional Independence Measure (FIM). ISNCSCI is the preferred instrument in clinical practice to assess the neurological deficit caused by the TSCI [SCIRE Professional, 2016]. For intubated TSCI patients, sedation will be lightened sufficiently to allow assessment, and this will be at the discretion of the local doctors.

The proposed primary outcome, the AIS Motor Score (AMS), is part of the ISNCSCI (also known as ASIA assessment) and is conducted by testing and scoring five myotomes in each limb, each rated 0 – 5, giving a total score between 0 – 100. Changes in motor scores or equivalent have been used widely in SCI trials including RISCIS (NCT01597518, Δ AMS 0 – 6 months), NISCI (NCT03935321, upper limb Δ AMS 0 – 6 months), MASC (NCT01828203, Δ AMS 0 – 3/6/12 months), MAPS (NCT02232165, Δ AMS 0 – 12 months) and CSFD (NCT02495545, Δ AMS 0 – 6 months).

ISNCSCI requires physical examination of the patient by a competent examiner (such as a physiotherapist) rather than a simple telephone assessment. We will require examiners to provide evidence that they have been trained, e.g. by completing the International Standards Training course (<https://lms4.learnshare.com/dashboard/dash.home.aspx?Z=0itApFGWTBr1Dh0rqKXQPSEwXn9LfMnB173Qk7jP5PM%3d&LSMID=>). The consensus from the patient focus groups is improvement in motor function as assessed by the AMS is a more meaningful outcome to patients in this setting than assessment by a HRQoL questionnaire. Participants in the trial will have the ISNCSCI examination performed on admission before surgery by neurosurgeons at the MTC (prior to randomisation) and at 6 months as part of their routine assessments at the spinal injuries unit by a physiotherapist or rehabilitation doctor. Therefore, the primary outcome measure is within the current standard of care and widely acceptable in the field to both patients and clinicians.

SECONDARY OUTCOMES (NEUROLOGY):

1. Change in AIS sensory score (light touch) at 6 months compared with baseline.
2. Change in AIS sensory score (pin prick) at 6 months compared with baseline.
3. Change in AIS grade at 6 months compared with baseline.

1. – 3. are standardised tools. We will quantify sensation (light touch, pinprick) using standard scales at 6 months versus baseline. The sensory outcomes are part of the ISNCSCI assessment and are conducted by testing and scoring 28 dermatomes on the left and 28 on the right as 0 (no sensation), 1 (reduced sensation) or 2 (normal sensation) giving a total score 0 – 112 for light touch and 0 – 112 for pinprick. From the ISNCSCI assessment, we will derive the AIS grade (A, B, C, D, E) as defined in the Table.

GRADE	DEFINITION	EXPLANATION
A	Complete	No sensory or motor function is preserved in the sacral segments S4-5.
B	Sensory Incomplete	Sensory but not motor function is preserved below the injury level and includes the sacral segments S4-5 (light touch or pin prick at S4-5 or deep anal pressure) AND no motor function is preserved more than three levels below the motor level on either side of the body.
C	Motor Incomplete	Motor function is preserved at the most caudal sacral segments for voluntary anal contraction OR the patient meets the criteria for sensory incomplete status by light touch, pin prick or deep anal pressure, and has some sparing of motor function more than three levels below the ipsilateral motor level on either side of the body. <50 % of key muscle functions below the level of injury have muscle grade ≥ 3 .
D	Motor Incomplete	Motor incomplete as defined above, with ≥ 50 % of key muscle functions below the neurological level of injury having muscle grade ≥ 3 .
E	Normal	Sensation and motor function graded as normal in all segments.

SECONDARY OUTCOMES (FUNCTION):

4. CUE-Q (to assess upper limb function) at 6 months.
5. Hand grip strength using a dynamometer at 6 months.
6. WISCI-II (to assess walking ability) at 6 months.
7. SCIM-III (to assess self-care and daily living) at 6 months.

SECONDARY OUTCOMES (QUALITY OF LIFE):

8. SF-36 at 6, 12 months.

4. – 8. are standardised tools. We will use these functional scales, which are established in TSCI, to confirm that the motor improvement that we seek is associated with functional improvements: CUE-Q (hand function), grip strength, WISCI II (walking) and SCIM III (independence measure that includes sphincter function and validated in TSCI). In addition, we use one a HRQoL scale as a secondary outcome measure (SF-36,) aiming to show that the functional improvement translates to improvement in HRQoL.

SECONDARY OUTCOMES (SAFETY)

9. Number of re-operations required on the spine within 12 months
10. Total length of hospital stay (Stay in MTC, stay in spinal injury unit, other hospital admissions)
11. Surgical complications and adverse events – recorded postoperatively and at follow-up visits
12. Overall survival (OS) – time from randomisation to death or end of follow-up (1 year)
13. MRI 2 weeks: Size of pseudomeningocele
14. MRI 6 months: Spinal deformity (Cobb angle between superior C2 and inferior C7 endplates); Size of pseudomeningocele,

9. – 12. are objective measures that yield the same value independent of assessor. 14. (spinal deformity) Is a standardised tool. Safety of duroplasty will be assessed in different ways, not only by comparing complications and adverse events, but also by determining the number of re-operations on spine, total hospital stay, OS as well as spinal deformity in the duroplasty versus the non-duroplasty arms.

SECONDARY OUTCOMES (MECHANISM):

15. MRI at 2 weeks (all patients):

- a. Length of cord compression (no CSF around the cord in mid-sagittal MRI)

16. MRI at 6 months (all patients):

- a. Length of cord tether
- b. Length of cord syrinx

17. Pressure monitoring at injury site (mechanistic study patients):

- a. Mean daily ISP
- b. Mean daily SCPP

18. MD monitoring at injury site (mechanistic study patients):

- a. Mean daily metabolites (glucose, lactate, pyruvate, LPR, glutamate, glycerol)
- b. Mean daily cytokines (GRO α , IL1 α , IL1 β , IL4, IL8, IL10, IP10, MCP1, MIP1 α , MIP1 β) or others.

15. and 16. are not standard measures because they are particular for DISCUS and will be measured on MRI by two radiologists. 17. and 18. are objective measures independent of assessor. The aim is to determine the mechanism by which duroplasty improves outcome. We will investigate if dural + bony decompression more effectively decompresses the swollen cord than bony decompression alone, i.e. lower ISP, higher SCPP, CSF around injured cord (MRI). More effective decompression by duroplasty is predicted to improve spinal cord metabolism, compared with bony decompression alone, i.e. more energy (higher glucose), less ischaemia (lower lactate, higher pyruvate and lower LPR), less excitotoxicity (lower glutamate) and less cell death (lower glycerol). More effective decompression by duroplasty is also predicted to reduce cord inflammation, compared with bony decompression alone, i.e. lower GRO α , IL1 α , IL1 β , IL4, IL8, IL10, IP10, MCP1, MIP1 α , MIP1 β . In the long-term (6 months), the extra space created by duroplasty is predicted to reduce cord tethering at the injury site and spinal cord syrinx.

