- C – Standard of care surgery within 72 hours of injury to include laminectomy spanning the length of swollen cord on the pre-operative MRI without duroplasty.

- O – Improvement in AIS motor score at 6 months compared with AIS motor score (AMS) at baseline (Δ AMS).

MECHANISTIC STUDY: DISCUS includes an optional study (led by [name]) to determine the underlying mechanisms by which duroplasty improves outcome, i.e. whether expansion duroplasty reduces cord compression, improves cord perfusion, reduces cord ischaemia and reduces cord inflammation. Any patient recruited into DISCUS is eligible for the mechanistic study; whether the patient participates in the monitoring study at a particular centre depends on whether the local neurosurgery unit / ICU elect to carry out ISP monitoring or MD monitoring or both. All neurosurgery units have equipment to monitor pressure, which is routinely used for severe brain injuries, and therefore ISP monitoring should be straightforward. Only some neurosurgery units have equipment to monitor MD. DISCUS will not purchase equipment for the mechanistic study but will contribute funds to cover costs of pressure probes and MD catheters and solutions.

- P – Patients \geq 16 years old with acute, severe TSCI.
- I – Patients will have surgery within 72 hours of TSCI including laminectomy spanning the length of swollen cord on the pre-operative MRI as well as dorsal duroplasty by suturing an elliptical patch of artificial dura about 1 cm longer than the dural incision and about 2 cm wide to the dural edge. A pressure probe and/or a MD catheter will be inserted intradurally at the injury site.
- C – Standard of care surgery within 72 hours of injury to include laminectomy spanning the length of swollen cord on the pre-operative MRI without duroplasty. A pressure probe and/or a MD catheter will be inderted intradurally at the injury site.
- O – Mean daily values of ISP, SCPP, injury site metabolites, injury site cytokines

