3.5 Secondary endpoints/outcomes

- Change in AIS sensory score (light touch) at 6 months compared with baseline (all patients)
- Change in AIS sensory score (pin prick) at 6 months compared with baseline (all patients)
- Change in AIS grade at 6 months compared with baseline (all patients)
- CUE-Q (upper limb function) at 6 months (all patients)
- Grip strength (hand function) at 6 months (all patients)
- WISCI-II (walking ability) at 6 months (all patients)
- SCIM-III (self-care and daily living) at 6 months (all patients)
- SF-36 at 6 and 12 months (all patients)
- Number of re-operations required on the spine within 12 months (all patients)
- Total length of hospital stay (Stay in MTC, stay in spinal injury unit, other hospital admissions) (all patients)
- Surgical complications and adverse events – recorded postoperatively and at follow-up visits

- OS – time from randomisation to death or end of follow-up (1 year) (all patients)
- MRI at 6 months: Spinal deformity (Cobb angle between the superior endplate of C2 to the inferior endplate of C7) (all patients)
- MRI at 2 weeks: Length of cord compression (no CSF around the cord in mid-sagittal MRI), Size of pseudomeningocele
- MRI at 6 months: Length of cord tether, Length of cord syrinx (all patients), Size of pseudomeningocele
- Pressure monitoring at injury site: Mean daily ISP, Mean daily SCPP (mechanistic study patients)
- MD monitoring at injury site: Mean daily metabolites (glucose, lactate, pyruvate, LPR, glutamate, glycerol), Mean daily cytokines/chemokines (GRO α , IL1 α , IL1 β , IL4, IL8, IL10, IP10, MCP1, MIP1 α , MIP1 β , or others) (mechanistic study patients)

Objective	Outcome Measure	Timepoint(s) of evaluation of this outcome measure
PRIMARY: To determine if bony + dural decompression improves motor score	Change in AIS motor score	6 months minus baseline
SECONDARY 1: To determine if bony + dural decompression improves neurological outcome	Change in AIS sensory score (light touch)	6 months minus baseline
	Change in AIS sensory score (pin prick)	6 months minus baseline
	Change in AIS grade	6 months minus baseline
SECONDARY 2: To determine if bony + dural decompression improves functional outcomes	CUE-Q	6 months
	Grip strength	6 months
	WISCI-II	6 months
	SCIM-III	6 months
SECONDARY 3: To determine if bony + dural decompression improves quality of life	SF-36	6, 12 months

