8 TRIAL TREATMENTS

DUROPLASTY: All patients will undergo surgery that involves spinal fixation and bony decompression including laminectomy. The surgical approach (anterior *versus* posterior fixation, no. of levels) is at the discretion of the local clinicians as are the target physiological parameters during surgery (blood pressure, arterial CO₂, O₂ etc.). However, the study requires that patients also have laminectomy spanning the levels of swollen cord based on the MRI, which requires a posterior approach.

Patients randomised to the duroplasty arm will also undergo expansion duroplasty, dorsally, under the same general anaesthetic. Therefore, patients will undergo either a posterior approach only (lateral mass screw fixation + laminectomy +/- duroplasty) or combined anterior and posterior approach. In the latter case, the surgeon may elect to fix anteriorly and posteriorly (so called 360-degree fixation) or only fix anteriorly and perform laminectomy +/- duroplasty posteriorly without additional fixation.

We recommend that a wound drain be placed on gravity and the skin be sutured and covered with waterproof adhesive film dressing e.g. IOBAN, an iodine impregnated dressing that minimises the risk of wound infection and of CSF leak. The wound drain and dressing are normally removed at 1 week and the sutures at 2 weeks. CSF leak is normally treated by placing extra sutures or a lumbar drain. Though neurosurgeons are familiar with duroplasty, the technicalities of the procedure will be discussed at the initial site visit and by detailed online training modules. The length of the duroplasty will span the length of the swollen cord estimated from the preoperative MRI. Duroplasty will be performed by suturing an elliptical patch of artificial dura about 1 cm longer than the dural incision and about 2 cm wide to the dural edge [Phang et al., 2015].

MONITORING PROBES: The patients for the mechanistic studies will also have a pressure probe and/or a MD catheter inserted intradurally posteriorly at the site of injury for up to 5 days and removed in ICU. Probe insertion is done at the time of surgery to fix the spine. Each probe is tunnelled through the skin and soft tissue, inserted through the dura with the tip positioned at the site of maximum swelling [Werndle et al., 2014; Phang et al., 2016]. The technicalities of probe insertion, tunnelling, suturing to the skin and removal will be discussed at the initial site visit and by detailed online training.

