9.3 Operational definitions for (S)AEs

The following will be reported by site as an SAE reportable to the central team within 24 hours:

- Death: only if deemed potentially directly related to duroplasty or probes (for example meningitis from CSF leak).
- Meningitis (defined as fever + symptoms/signs of meningism + elevated CSF neutrophil count and positive CSF microbiology culture)

- Redo spinal surgery: only if deemed potentially directly related to duroplasty or probes (e.g. repair of CSF leak, removal of retained probe)
- Worsening of AIS grade: only if deemed potentially directly related to duroplasty or probes
- Wound infection that requires antibiotics: only if deemed potentially directly related to duroplasty or probes
- Wound breakdown that requires surgical debridement: only if deemed potentially directly related to duroplasty or probes (i.e. wound breakdown from deep infection)

EVENTS EXEMPT FROM BEING REPORTED AS SAEs

The following are complications and collected as outcome and do not require SAE reporting:

- Death: related to reasons other than duroplasty or probes (e.g.: *deaths related to pulmonary embolus*)
- Repair of CSF leak not requiring general anaesthetic (e.g. *Lumbar drain insertion, Re-suturing of wound of probe site*)
- Redo spinal surgery unrelated to duroplasty or probes (e.g. *evacuation of haematoma, surgery for: Metalwork failure, Deformity correction, Removal of metalwork, Syrinx*)
- Worsening of AIS grade (*If deemed NOT related to duroplasty or probes, this does not need reporting and will be picked up in 6-month ISNCSI/assessment*)

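### Research probes breach the dura in at least 25 controls, so the all-patient safety comparison may understate the CSF-related effect of duroplasty, and SAE relatedness does not separate the two causes

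*Protocol*

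**What the plan says.** Protocol Section 3.3 states the safety aim: "Safety of duroplasty will be assessed in different ways, not only by comparing complications and adverse events". The same sentence goes on to re-operations, hospital stay and survival, and ends "as well as spinal deformity in the duroplasty versus the non-duroplasty arms". Section 3.5 labels the re-operation outcome as covering all patients. Complications and adverse events carry no restriction to unmonitored patients.

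Mechanistic-study controls receive probes without duroplasty. Section 2 says of the control group: "A pressure probe and/or a MD catheter will be inderted intradurally at the injury site". Section 8 describes each probe as "inserted through the dura with the tip positioned at the site of maximum swelling". Section 4 sets a minimum of 50 monitored patients, at least 25 per arm. Section 10.1 says the number may exceed 50 and sets no cap.

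Section 2.1 says of monitoring: "The most common complications are CSF related and easy to manage by adding extra sutures to the wound or spontaneously resolve". It also describes the commonest complications of duroplasty as CSF-related.

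Section 9.2 has one causality rating against the trial intervention. Section 9.3 makes most listed events reportable by reference to duroplasty and probes jointly, for example "Death: only if deemed potentially directly related to duroplasty or probes". Age group and country are the only minimisation factors (Section 7.3). Section 10.3.3 names chi-squared tests and logistic regression for binary outcomes, adjusted for baseline and minimisation factors.

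**The concern.** If duroplasty is adopted, it will be done without research probes. The safety figure of interest is therefore duroplasty against no duroplasty in patients whose dura is not otherwise opened. A control with a probe is not such a patient. The probe breaches the dura, and on the protocol's own figures it carries a pseudomeningocele rate close to that of duroplasty.

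Pooling monitored and unmonitored patients mixes two contrasts: duroplasty against an intact dura, and duroplasty plus probe against probe alone. How far the pooled figure departs from the first contrast depends on the share monitored, which is open-ended, and on how the two risks combine, which is unknown. Safety is a stated objective, and Section 1 expects immediate NHS-wide use if benefit is shown. A CSF-related difference that is partly an artefact of sub-study uptake would then matter.

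Attribution is a separate problem. If relatedness is collected once for both procedures, an analysis cannot reliably separate them later in a patient who had both.

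**Working it through.** **Inputs (Protocol)**
- Arm size: 222 at 1:1, so 111 per arm (Sections 4, 10.1).
- Probed: 25 per arm (Section 4), so f = 25/111 = 22.5%.
- Duroplasty risk D (Section 2.1): pseudomeningocele 5/26 = 19.2%; CSF leak 4/26 = 15.4%.
- Probe risk P (Section 2.1): pseudomeningocele 8/42 = 19.0%; CSF leak 3/42 = 7.1%.
- Background risk without a dural opening: not given. Taken as 0 for risk differences, and as 2% and 5% for odds ratios.

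**The plan's own figures.** A difference of 11 with SD 25, two-sided 5% and 85% power needs 94 per arm by t-test. Then 188/0.85 = 221.2, which gives 222 in two equal arms. The printed 19%, 19% and 7% reproduce. The printed 10% for CSF leak after duroplasty does not, since 4/26 is 15.4%; I use the count.

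**Risk difference.** Let J be the risk with both duroplasty and a probe, and let a share f of each arm be probed.
- Control arm: fP
- Duroplasty arm: D + f(J − D)
- All-patient difference: D − f(P + D − J)

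The shortfall against the probe-free difference D is f(P + D − J). Three cases:
- Probe adds nothing to duroplasty (J = D): shortfall fP
- Independent risks (J = D + P − DP): shortfall fDP
- Additive risks (J = D + P): shortfall 0

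| Outcome | Probe-free difference | J = D | Independent | Additive |
|---|---|---|---|---|
| Pseudomeningocele | 19.2 points | 14.9 (22% too small) | 18.4 (4%) | 19.2 (0%) |
| CSF leak | 15.4 points | 13.8 (10%) | 15.1 (2%) | 15.4 (0%) |

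For example, 0.225 × 19.0% = 4.3 points, and 4.3/19.2 = 22%. In counts, 25 probed controls would yield 25 × 8/42 = 4.8 pseudomeningoceles and 25 × 3/42 = 1.8 leaks.

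**Sensitivity**
- With 50 of 111 probed (an assumption), the shortfalls are 45%, 9% and 0% for pseudomeningocele and 21%, 3% and 0% for CSF leak.
- The 8/42 is imprecise (95% CI 8.6–34.1%). If the 42 include the 10 exploratory duroplasty patients and their 5 pseudomeningoceles (an assumption), the probe-only rate is 3/32 = 9.4%. The largest shortfall is then 0.225 × 9.4% = 2.1 points (11%).
- With the printed 10% for duroplasty CSF leak, the largest shortfall is 1.6 of 10 points (16%).

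**Odds ratio (pseudomeningocele, 25 of 111 probed).** Background 2%, with probes adding 19.0 points in controls:
- Unmonitored: (0.192/0.808)/(0.02/0.98) = 11.7
- All-patient control risk: 2% + 4.3% = 6.3%
- All-patient odds ratio: 3.6 (J = D), 4.4 (independent), 4.6 (additive)

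With a 5% background, 4.5 falls to 2.3, 2.9 and 3.0. With the 3/32 probe rate, 11.7 falls to 5.6–6.3 and 4.5 to 3.1–3.5. The odds ratio is attenuated even when the risk difference is not.

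**The case against.** The strongest objection is that the duroplasty arm is probed too. If the risks add, the extra events cancel and the risk difference is unbiased. This stands, and it is why the ranges above start at zero. Additivity is also plausible for CSF leak, because a probe is tunnelled through the skin and has its own leak site.

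The source rates are weak. The 5/26 matches the 50% of 10 duroplasty patients in the exploratory study (Section 2). That study compared ISP between its groups, so those patients must have been monitored. The 19% is then not a probe-free rate. The bias on the difference scale reverses once J exceeds 19.2% + 19.0%, about 38.3%, and 5 of 10 lies above that. The numbers are tiny, but they rule out a firm claim about direction.

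It can also be said that strata belong in the SAP, and that probe dates, CSF leak and pseudomeningocele are already recorded (Section 7.6). That is fair for the analysis, and the absence of a stratified analysis from the protocol is not counted here as an error. It does not answer the attribution point. A single causality rating and a joint reporting trigger are set by the protocol, and CSF leak is recorded yes/no without a source. Free-text case descriptions for SAEs help only in part.

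A reader might infer that the trial will understate the harm of duroplasty, or that every safety outcome is affected. The documents support neither reading. The direction is not determined, and they show no route from probes to survival, hospital stay or Cobb angle.

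**Conclusion.** The point holds in a limited form. The all-patient comparison may understate the CSF-related effect of duroplasty as it would be practised without probes. At the planned minimum of 25 of 111 per arm, the risk difference is 0–22% too small for pseudomeningocele and 0–10% for CSF leak. The upper ends require that probes add nothing once the dura has been opened for duroplasty; more-than-additive risks would reverse the sign. Odds ratios, the scale of the logistic model named in Section 10.3.3, move towards 1 even if the risks add.

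These figures assume equal probe use in both arms, no background events (2% or 5% for odds ratios), and small series that may overlap. They concern occurrence of an event, not pseudomeningocele size. The pooled relatedness item is the part that the protocol itself fixes badly. This is a cheap improvement and not a fault that undermines the trial.

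**What to change.** Keep the all-patient safety comparison, and adjust it for mechanistic-study participation. Also report CSF leak, pseudomeningocele, meningitis and CSF-related re-operation by arm within the monitored and unmonitored strata. Adjustment alone is not enough, because it averages over the two contrasts.

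Define the strata before randomisation, by consent to monitoring (already marked on the consent form, Section 7.2.1) or by a logged intention to monitor. The log is needed for emergency enrolments, which Section 7.2 allows without prior consultee advice. Strata defined by probes actually inserted would depend on events after randomisation.

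On the complication and SAE forms, record relatedness to duroplasty and relatedness to probes as two items, and align Sections 9.2 and 9.3 with this.

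The cost is one extra form item, analysis wording, and wider intervals within strata. If 50 are monitored, those in the unmonitored stratum are about 14% wider (√(222/172) = 1.14), and those in the monitored stratum about twice as wide (√(222/50) = 2.1). Making the unmonitored stratum the main safety estimate is not proposed, because it would set aside at least 50 randomised patients when some of the events are rare.
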